2.1 Cluster headache

Trigeminal autonomic cephalalgias (TACs) are characterized by frequent, shortlasting attacks of unilateral extremely severe headaches accompanied by ipsilateral facial autonomic features and are the most severe of the primary headache disorders (1). TACs include cluster headache (CH), paroxysmal hemicrania (PH) and shortlasting unilateral neuralgiform headache with conjunctival injection and tearing (SUNCT) (3;4). CH is the most common form of TAC. The 1-year prevalence is about 1 in 1000, with the vast majority of patients having episodic CH (ECH): periods of weeks to months with frequent attacks which are alternated with symptom-free periods of several months to years. About 10% have chronic CH (CCH): attack free periods of less than one month in every 12 months, unless treatment is given. The chronic form can be primary unremitting from onset, or can be secondary, transform from the episodic form. CCH may spontaneously become episodic.

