A similar design was successfully used in a multicenter, prospectively randomised, parallel, double-blind study that showed that high vagus nerve stimulation gave significantly more reduction in seizure frequency than low vagus nerve stimulation (24). This finding supports a proposed dose response in neurostimulation and subsequently supports our design. Supposed treatment allocation by the patient, on the other hand, was not mentioned in this study.

Matharu et al. (25) showed a correlation between mean pain scores, stimulator induced paresthesia and changes in regional cerebral blood flow in ONS treated chronic migraine patients. These findings suggest a dose related effect of the stimulation and thereby supports our design.

Blinding

Patients, neurologists and the study investigator will be blinded for the randomisation. The IPG programming (not blinded) will be performed by the implanter (neurosurgeon or anaesthesiologist) or research nurse. They will take precautions to ensure that patients are unaware of their randomisation status by not informing them about the stimulation conditions.

Protocol: Occipital nerve stimulation in medically intractable, chronic cluster headache CME Protocol number: 10.016

Follow-up

Follow-up second period

			V	'ersio	n 1.1	1 dd. 26	5-09-2	2018			I														
T=6	12 months	after	surgery		+ 4	weeks							X		X						X		X		
T=5	9 months	after	surgery		± 4	weeks							Х		Х								Х		
T=4	6 months	after	surgery		± 2	weeks							Х		X			Х			Х		Х		
T=3	4 months	after	surgery		± 2	weeks							Х		Х								Х		
T=2	2 months	after	surgery		± 1 week								Х		Х								Х		
T=1	1 month	after	surgery		± 1 week								Х		Х								Х		
T=0	10 days	after	surgery		± 2 days						Х				Х								Х		
T=-1	Interventio	n								X	X				Х								X		
T=-2	Pre-op 3	months	after	inclusion									Х					Х					Х		
T=-3	Inclusion	start	electronic	diary			Х						Х										Х		
					Visit	Window	Patient	characteristi	cs	Intervention	Wound	inspection	Headache	diary	Stimulation	and system	check	Economic	evaluation	questionnaire	Patient	satisfaction	Adverse	events	

5. Patient recruitment

Patients will be recruited from tertiary headache clinics in The Netherlands, Denmark,

UK and probably Belgium and Germany.

6. Study Purpose

Objectives

The primary objective of this study is to investigate whether ONS reduces the attack frequency in MICCH compared to baseline.

7. Endpoints

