16.1 The aim of the study

[1] to prove that the treatment has a beneficial effect over follow-up time since start of treatment

[2] after [1] has been established, to prove that there is a dose-response effect.

While (1) may be ascribed (at least in part) to a placebo effect, we believe that (2) cannot, since its associated effect measure is based on a between group comparison with random allocation to which the patient should be sufficiently blinded.

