16.2 Endpoints

The primary endpoint is the mean attack frequency (MAF). Let MAF0 and MAF6 denote the MAF at baseline and the MAF at six months for a given patient. MAF0 is the baseline value for each individual patient of the primary endpoint and hence will be taken into account in the analyses as a covariate; although the primary comparison is a randomised one and MAF0 strictly speaking does not need to be taken into account, incorporating this value into the analyses will increase power and allows secondary analyses with respect to possible interaction between the treatment and the baseline level.

The MAF has a skewed distribution, and therefore we will take the (natural) logarithm in our analyses. If case MAF6 is equal to zero, we will add the minimal possible value of 0.25 (corresponding to a single attack per month) to allow taking the logarithm.

The analyses will take the general shape of a regression analysis with lnMAF6 as the dependent variable, lnMAF0 as the covariate and treatment as a fixed factor. An interaction between treatment and lnMAF0 will be added in a secondary analysis.

We assume the following model: $\ln MAF6 = a + b \ln MAF0 + c \operatorname{Treat}$, where Treat=0 for 30% stimulation and Treat=1 for 100% stimulation, thus being an indicator variable for the randomly allocated arm.

First we use an F test to evaluate (at the 5% level) the null-hypothesis

(1) H₀1: a=0 & b=1 & c=0

(effectively comparing this model to the null-model: lnMAF6=lnMAF0 in both randomised groups)

Rejection of this null-hypothesis means that we have confirmed a stimulation effect over time. Now, ONLY if (1) is rejected, do we test the following three nullhypotheses

(2a) H₀2a: a=0 & b=1 conditional on Treat=0 (30% stimulation)
(2b) H₀2b: a=0 & b=1 conditional on Treat=1 (100% stimulation)
(2c) H₀2c: c=0 (no stimulation intensity effect)

Rejection of (2c) means that we have confirmed a dose-response effect, in other words a difference between 30% and 100% stimulation.

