16.4 Power and sample size

Because of limited information about the distribution of the MAF for our specific group of patients, we conducted a small pilot study. We found a MAF of 26.42 attacks per week, with a standard deviation of 15.38. These findings did not differ very much from figures given by Burns et al. (7). These numbers correspond to lnMAF having a a mean of 3.13 and a standard deviation of 0.54.

We expect (MAF6 – MAF0) to be -9 on average in the 100% stimulation group, while we expect no reduction in the 30% stimulation group. This corresponds to (\ln MAF6 – \ln MAF0) being -0.42 on average in the 100% stimulation group.

If we assume that lnMAF0 and lnMAF6 are positively correlated, then the standard deviation of Delta = (lnMAF6-lnMAF0) would be in the range from 0.54 to $\sqrt{2}$ *0.54=0.76. Powering in terms of this Delta is a fair approximation to the regression analysis model; in fact, if the coefficient b would be equal to 1, the calculations would be identical.

Note that tests (1), (2a) and (2b) are in essence paired tests, comparing for each patient a change with respect to baseline. Test (2c) is an independent, two sample test because we compare the two treatment arms. Consequently, the test for (2c) will be the least powerful and so we performed our power analysis for that test. We did verify that all other tests are more powerful.

We attach the results of our power analysis. We conclude that if the standard deviation is 0.54 and the average of (lnMAF6-lnMAF0) is about -0.42, then 60

Protocol: Occipital nerve stimulation in medically intractable, chronic cluster headache CME Protocol number: 10.016 Version 1.11 dd. 26-09-2018 patients in each arm will allow us to detect the difference with probability 98%.

Taking a possible 20% drop-out rate into account, we propose a total study size of 144 divided equally between both arms.

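### Section 6 and section 16.2 rest a claim of a stimulation effect on change from baseline, which in a trial where every patient is stimulated cannot be attributed to stimulation; only test (2c) is randomised

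*Combined protocol and SAP*

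**What the plan says.** The plan describes its main question in two ways.

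- **Change from baseline.** Section 6: "The primary objective of this study is to investigate whether ONS reduces the attack frequency in MICCH compared to baseline". Aim [1] in section 16.1 is "to prove that the treatment has a beneficial effect over follow-up time since start of treatment". Section 16.2 begins the testing with this question: "First we use an F test to evaluate (at the 5% level) the null-hypothesis" a=0, b=1, c=0, which it explains as "effectively comparing this model to the null-model: lnMAF6=lnMAF0 in both randomised groups". It then states: "Rejection of this null-hypothesis means that we have confirmed a stimulation effect over time". Section 16.4 says that "tests (1), (2a) and (2b) are in essence paired tests, comparing for each patient a change with respect to baseline".
- **Randomised comparison.** Sections 1 and 4 describe a trial comparing 100% with 30% stimulation, and section 7.1 defines the primary endpoint in those two groups. Section 16.2 itself calls the primary comparison randomised, and section 16.4 sizes the trial on (2c), the between-arm test.

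Section 16.1 also limits the first question: "While (1) may be ascribed (at least in part) to a placebo effect, we believe that (2) cannot". That caveat is not repeated in section 6 or attached to the decision rule in 16.2.

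**The concern.** Both arms receive an implant and stimulation. A fall from baseline can therefore come from stimulation, but also from placebo response, surgery, monthly neurologist contact, the changes in prophylactic dose that section 8.1 allows, or natural course. On the last, section 2.1 says that "CCH may spontaneously become episodic". No unstimulated group exists against which to subtract these.

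Section 1 gives as background that earlier studies were not randomised and could not exclude a placebo effect. A primary objective framed as change from baseline has the same weakness. If both arms improve alike and (2c) is not significant, the text of 16.2 would still call a stimulation effect confirmed, although 16.1 says the same result may be placebo.

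**Working it through.** **1. The plan's own figure.** Inputs from section 16.4: MAF 26.42 (SD 15.38), expected change −9 in the 100% arm and none in the 30% arm, 60 per arm.

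- Log scale: SD = √ln(1 + (15.38/26.42)²) = 0.54; mean = ln 26.42 − 0.54²/2 = 3.13; effect = ln(17.42/26.42) = −0.42. All three match the plan.
- Power of (2c), two-sided 5%, SD 0.54: 0.42 / (0.54 × √(2/60)) = 4.26, giving 98.8% (noncentral t) or 98.9% (normal). The plan says 98%, so the figure is reproduced.
- At the plan's upper SD of 0.76: 0.42 / (0.76 × √(2/60)) = 3.03, giving 85.1% or 85.7%.

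**2. What test (1) does when stimulation has no effect.** Let both arms fall by the same amount f on the log scale, with b=1 and c=0, so that lnMAF6 − lnMAF0 = −f + error, and the error SD is the SD of Delta (0.54 to 0.76, section 16.4). The constant −f lies within the fitted model, so the F statistic for a=0, b=1, c=0 has 3 and 120 − 3 = 117 degrees of freedom and noncentrality

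λ = 120 × f² / SD².

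The 5% critical value is 2.68. The values of f are assumptions.

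| f (log) | Fall, 1 − exp(−f) | λ, SD 0.54 | (1) rejects | λ, SD 0.76 | (1) rejects |
|---|---|---|---|---|---|
| 0.15 | 14% | 9.26 | 71% | 4.67 | 40% |
| 0.20 | 18% | 16.46 | 93% | 8.31 | 66% |
| 0.30 | 26% | 37.04 | 100% | 18.70 | 96% |

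Simulation of the same F test gave 70%/39%, 93%/65% and 100%/96%, which agrees to within about one point.

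**3. What test (2c) does in the same situation.** A fall common to both arms cancels between arms. Simulated rejection of (2c) after passing (1) stayed at about 5% or below (b=1, common falls from 0 to 34%).

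**4. What test (1) contains.** Its null hypothesis includes c=0. A true difference between arms can therefore reject it with no average change from baseline. It is a joint test, and only its a and b components are before-after. Tests (2a) and (2b) are entirely before-after within one arm.

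**5. Cost of the gate to (2c).** With the planned effect and b=1, simulated power of (2c) alone and of (2c) after rejecting (1) was 98.7% and 98.7% at SD 0.54, and 86.2% and 84.7% at SD 0.76.

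**The case against.** The strongest reply is that the plan, read as a whole, already ranks its evidence correctly. Section 16.1 concedes the placebo contribution just before the tests are set out. Section 16.2 calls the primary comparison randomised, section 16.4 powers (2c), and (2c) is unaffected by any common fall. Section 6 asks only about change from baseline, which a before-after test does answer. Section 8.1 also bars new prophylactic and other cluster headache treatments, section 16.5 stops data collection at a switch to steroids, and eligibility is rechecked after a 12-week diary. These rules limit non-specific change.

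Much of this stands. The trial has a valid controlled comparison, adequately powered on the plan's inputs. Several stronger readings are tempting but not supported:

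- *That the sponsor would report equal falls as proof that the treatment works.* No section defines trial success or says how a result with (1) rejected and (2c) not rejected would be reported.
- *That equal falls would show a placebo effect.* Both arms are active. Equal falls could equally mean that both intensities work.
- *That (1) is purely an uncontrolled comparison.* It includes c=0.
- *That the rejection rates are those of a simple paired t-test.* That test would give 86%/57% for a 14% fall, but the plan uses the 3-df F test, which gives 71%/40%.
- *That the gate must be removed.* It does not inflate the error of (2c) and costs little power.

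The reply does not remove the core point. The 16.1 caveat is absent from section 6 and from the 16.2 rule, and a result that may be placebo cannot also confirm a stimulation effect. The rules on concomitant treatment reduce non-specific change but do not exclude it.

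**Conclusion.** The point holds as a defect in the stated objective and in the inference attached to test (1). Sections 6 and 16.2 conflict with 16.1 and with the randomised comparison in sections 1 and 4 and in 16.2 itself. With no stimulation effect and an equal fall in both arms, the sentence in 16.2 would be triggered in about 40% to 71% of trials for a 14% fall, 66% to 93% for 18%, and 96% to 100% for 26%.

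These figures assume 120 analysed patients, b=1, normal errors and an SD of Delta from 0.76 down to 0.54. The size of the common fall is assumed; section 16.4 expects none at 30% stimulation. Test (2c) is sound on this point and needs no repair.

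**What to change.** 1. **Section 6.** State the primary objective as the randomised comparison of lnMAF6 between 100% and 30% stimulation, test (2c). Describe (1), (2a) and (2b) as assessments of change from baseline, noting that (1) also responds to a difference between arms.
2. **Section 16.2.** Replace the sentence on rejection of (1) with:

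> Rejection of (1), (2a) or (2b) shows a change from baseline or a difference between arms; change from baseline alone cannot be attributed to stimulation. Only (2c) is a randomised test of a stimulation-intensity effect. If (2c) is not rejected, equal falls may reflect placebo, natural course or equal efficacy of both intensities, and the trial cannot distinguish these.

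3. **Section 16.1.** Reword aim [1] so that it no longer speaks of proof of benefit.
4. **Optional.** If (2c) becomes the single primary test, it can be tested at 5% without first rejecting (1). Section 16.3 would then need revision, because its closed-testing argument is built on (1). Keeping the gate is also acceptable.

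Items 1 to 3 change wording only, with no new patients, visits or data. The sample size is unaffected because section 16.4 already rests on (2c). The price is the loss of a within-arm efficacy claim that the design cannot support.

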16.3 Multi testing correction

We claim that upon rejection of (1), we may simultaneously test (2a), (2b) and (2c) at the 5% level, while maintaining the probability of falsely rejecting a single null hypothesis at 5% (so without the need for correction for multiple testing). This follows from the so-called closed testing principle (42). The underlying idea is that if null hypothesis (1) is false, then *at most one* of (2a), (2b) and (2c) can be true. The

Protocol: Occipital nerve stimulation in medically intractable, chronic cluster headache CME Protocol number: 10.016 Version 1.11 dd. 26-09-2018 closed-testing principle has been applied before in clinical trials but not very often (43). The method is more powerful than the more familiar "gate keeping" procedure, where we test hypotheses (1), (2c), (2b) and (2a) in order, and stop as soon as we fail to reject one.

The issue of multiple testing in biomedical research in general and in clinical trials in particular, is discussed by Bender and Lange (44).

16.4 Power and sample size

Because of limited information about the distribution of the MAF for our specific group of patients, we conducted a small pilot study. We found a MAF of 26.42 attacks per week, with a standard deviation of 15.38. These findings did not differ very much from figures given by Burns et al. (7). These numbers correspond to lnMAF having a a mean of 3.13 and a standard deviation of 0.54.

We expect (MAF6 – MAF0) to be -9 on average in the 100% stimulation group, while we expect no reduction in the 30% stimulation group. This corresponds to (\ln MAF6 – \ln MAF0) being -0.42 on average in the 100% stimulation group.

If we assume that lnMAF0 and lnMAF6 are positively correlated, then the standard deviation of Delta = (lnMAF6-lnMAF0) would be in the range from 0.54 to $\sqrt{2}$ *0.54=0.76. Powering in terms of this Delta is a fair approximation to the regression analysis model; in fact, if the coefficient b would be equal to 1, the calculations would be identical.

Note that tests (1), (2a) and (2b) are in essence paired tests, comparing for each patient a change with respect to baseline. Test (2c) is an independent, two sample test because we compare the two treatment arms. Consequently, the test for (2c) will be the least powerful and so we performed our power analysis for that test. We did verify that all other tests are more powerful.

We attach the results of our power analysis. We conclude that if the standard deviation is 0.54 and the average of (lnMAF6-lnMAF0) is about -0.42, then 60

Protocol: Occipital nerve stimulation in medically intractable, chronic cluster headache CME Protocol number: 10.016 Version 1.11 dd. 26-09-2018 patients in each arm will allow us to detect the difference with probability 98%.

Taking a possible 20% drop-out rate into account, we propose a total study size of 144 divided equally between both arms.

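### 16.2 takes rejection of hypothesis (1) as a confirmed stimulation effect, although regression to the mean alone can cause it; in 16.4, 144 patients leave about 57 per arm after 20% drop-out, not 60

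*Combined protocol and SAP*

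**What the plan says.** Section 16.2 models lnMAF6 = a + b lnMAF0 + c Treat. An F test of (1), a = 0, b = 1 and c = 0, comes first. If it is rejected, three further hypotheses are tested: (2a) and (2b), a = 0 and b = 1 within the 30% and the 100% arm, and (2c), c = 0. The interpretation given to the first step is: "Rejection of this null-hypothesis means that we have confirmed a stimulation effect over time". Section 16.1 adds one caution, "While (1) may be ascribed (at least in part) to a placebo effect", and relies on the randomised comparison for what placebo cannot explain. Section 6 makes reduction from baseline the primary objective.

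Section 16.4 sizes the trial on (2c), using Delta = lnMAF6 − lnMAF0. It takes a mean of −0.42 in the 100% arm, and for the other arm: "while we expect no reduction in the 30% stimulation group". It gives 0.54 to 0.76 as the range for the SD of Delta and concludes, at SD 0.54, that 60 "patients in each arm will allow us to detect the difference with probability 98" per cent. Then: "Taking a possible 20% drop-out rate into account, we propose a total study size of 144 divided equally between both arms".

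For attack-free patients, 16.2 states: "If case MAF6 is equal to zero, we will add the minimal possible value of 0.25 (corresponding to a single attack per month"). The text of 16.4 does not mention them. It does say "We attach the results of our power analysis", but that attachment is not in the text available here. Section 7.2 already plans a repeat of the primary analysis on untransformed MAF, and a responder rate. Neither needs a constant.

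**The concern.** The main problem is interpretive. The condition b = 1 is a statement about the slope, not about average benefit. When two measurements on the same patient are imperfectly correlated and equally variable, the slope is below 1 whether or not treatment works. A report following 16.2 could then announce a confirmed stimulation effect, on the primary objective, when mean attack frequency had not changed. The caution about placebo in 16.1 does not cover this.

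Two smaller matters sit in 16.4. The total of 144 does not deliver the 60 per arm on which the 98% is quoted. And the power statement is not examined against the 0.25 rule, under which one attack-free patient contributes a very large log change.

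**Working it through.** **Inputs from 16.4.** lnMAF mean 3.13, SD 0.54; difference 0.42; 60 per arm; 20% drop-out; total 144. Level 5% (16.3), taken as two-sided.

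**Reproducing the plan.** Lognormal moments of 26.42 and 15.38 give mean 3.13 and SD 0.54, and ln(17.42/26.42) = −0.417. The two-sample t power at 60 per arm, difference 0.42, SD 0.54 is 98.8%. The stated 98% reproduces.

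**Slope implied by 16.4.** With equal SDs of 0.54 and correlation ρ, SD(Delta) = 0.54 × √(2(1 − ρ)). The value 0.54 corresponds to ρ = 0.5 and 0.76 to ρ = 0. The slope then equals ρ, so the plan's own range implies b of 0.5 or less. With no mean change, a = 3.13 × (1 − ρ): at ρ = 0.5, a = 1.565 and b = 0.5. The mean change, a + 3.13b − 3.13, is zero, yet (1), (2a) and (2b) are all false.

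**How often they are rejected.** The systematic departure from lnMAF6 = lnMAF0 has variance (1 − ρ)² × 0.54² and the residual variance is (1 − ρ²) × 0.54², so the noncentrality is about n(1 − ρ)/(1 + ρ). For (1), with n = 114, this is 38.0, 20.1 and 6.0 at ρ = 0.5, 0.7 and 0.9. Within one arm, n = 57, it is 19.0, 10.1 and 3.0. Simulation (bivariate normal, equal means, SD 0.54, 57 per arm, at least 4,000 trials each) gives these rejection rates:

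| Test, no mean change in either arm | ρ = 0.5 | ρ = 0.7 | ρ = 0.9 |
|---|---|---|---|
| (1) | 100% | 96% | 50% |
| (2a) | 96% | 77% | 31% |
| (2b) | 96% | 78% | 31% |
| (2c) | 5% | 5% | 5% |
| Paired t-test of mean change | about 5% | about 5% | about 5% |

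**Drop-out.** 144 = 120 × 1.2, which covers a loss of 1 − 120/144 = 16.7%. With 20% loss, 144 × 0.8 = 115.2, or 57.6 per arm. Keeping 120 needs 120/0.8 = 150. Power at 57 per arm, SD 0.54, is 98.4%. The planned regression has residual SD 0.54 × √(1 − ρ²), at most 0.54, giving 98.4%, 99.1% and 99.7% at ρ = 0, 0.3 and 0.5.

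**Attack-free patients (shares assumed; none is given).** From the planning mean, a zero scored as 0.25 is a log change of ln(0.25) − 3.13 = −4.52. In the 30% arm, with share q, SD(Delta) = √(0.54² + q(1 − q) × 4.52²): 0.83 at 2% and 1.12 at 5%, above the 0.76 upper end in 16.4. Simulated power for (2c) with the primary regression, 57 per arm and ρ = 0.5:

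- Equal shares in both arms, the remaining patients differing by 0.42: about 80% at 2%, 54% at 5%.
- Zeros only in the 100% arm, on top of the 0.42 shift: near 100% at 5% and 10%. At 5%, c becomes 0.95 × (−0.42) + 0.05 × (−4.52) = −0.62. With 0.125 in place of 0.25 it becomes −0.66, since ln(0.125) − 3.13 = −5.21.
- Zeros only in the 100% arm, but with the total mean difference held at 0.42 (t-test on Delta): 94%, 80% and 52% at 2%, 5% and 10%.

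In a version with Poisson counts, the untransformed-MAF analysis keeps 98% and 96% power at equal shares of 2% and 5%.

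**The case against.** The best defence of 16.2 is that (1) is a well-defined null, that it really is false when b is below 1, and that rejecting it is therefore not a type I error. Section 16.1 also already discounts (1) for placebo and rests the causal claim on (2c). All of that stands. A reader might infer that the trial's error rate is inflated or that the closed test in 16.3 fails; neither follows. What does not stand is the conclusion that 16.2 draws from rejection.

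On 16.4, a reader might infer that the trial is underpowered after drop-out. It is not: the loss is about 0.4 points. Nor does SD 0.76 bring power down to 83% at 57 per arm for the planned test. That figure belongs to a t-test on Delta, and with lnMAF0 as covariate and equal SDs the residual SD cannot exceed 0.54. Section 16.4 itself calls its calculation an approximation: "Powering in terms of this Delta is a fair approximation to the regression analysis model".

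The most tempting overstatement is that the 98% holds only if nobody is attack-free. The documents do not support it. Section 16.4 does state its condition, SD 0.54 and a mean of −0.42, and zeros confined to the 100% arm on top of that shift keep power. Equal shares in both arms also depart from the plan's premise for the 30% arm: 5% would move its mean log change by 0.05 × (−4.52) = −0.23. The check on untransformed MAF is already planned, and the missing attachment may cover more than the text shows.

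**Conclusion.** The wording of 16.2 is wrong and should be changed. Under the plan's own figures, rejection of (1) is nearly certain with no mean change, and it remains about 50% at a correlation of 0.9. This rests on equal log-scale SDs at the two times, which 16.4 also uses; the correlation itself is not reported. Test (2c) and the order of testing are sound.

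The drop-out figure is a definite but minor slip: about 57 per arm, not 60, with power still about 98%.

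The 0.25 rule is a conditional point. Power for (2c) could range from near 100% to about 54% at assumed shares up to 5%, depending on which arm the attack-free patients are in. The documents do not settle this, so it is a matter for reporting and a named check, not evidence of a power shortfall.

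**What to change.** **16.2 and 16.1.** Replace the interpretation of (1) with: 'Rejection of (1), (2a) or (2b) shows a departure from lnMAF6 = lnMAF0. Because b = 1 is part of each, rejection does not by itself confirm a stimulation effect.' State that aim [1] is judged on the mean of lnMAF6 − lnMAF0 in each arm with its 95% CI. The test order and (2c) stay as they are.

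**16.4.** Replace the drop-out sentence with: '144 patients leave about 57 per arm after 20% drop-out; power for (2c) is still about 98% at SD 0.54 and a mean difference of 0.42.' No extra enrolment, and no clause about attack-free patients, since that would add an incorrect condition.

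**16.5.** Report the number with MAF6 = 0 per arm. Name the untransformed-MAF analysis of 7.2 as the check on (2c). Any re-run with another constant should use a value below 0.25, for example 0.125. A value such as 0.5 would score an attack-free patient worse than one with a single attack in 4 weeks.

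**Cost.** A few sentences and a little more analysis and reporting. The per-arm mean change remains an uncontrolled before-after comparison and also depends on the 0.25 rule. The two intervals lie outside the closed test: if neither arm changed, the chance that at least one excludes zero is about 1 − 0.95² = 9.75%, so the plan should say how they will be read.
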